5.3 ORIENTATION

Participants will attend an Orientation Visit during which the e-cigarette device power level order will be determined and study procedures will be described in detail again. The following will occur:

5.3.1 Product Assignment

Three e-cigarette device power levels will be assigned to all participants: low, medium, and high battery levels (10, 15, 20 Watts). The order of the assignment will be randomized, single-blinded.

E-liquid Selection: We will obtain the e-liquid from AVAIL, a leading premium e-liquid manufacturer and retail business which works with academic centers to provide research grade products that come with certificates of analysis confirming nicotine content, lack of diacetyl (<38 ppm) and acetyl propionyl (<100 ppm). We will purchase the most popular e-liquid from AVAIL at the time of the study and will contain 12 mg/mL.

E-cigarette Device: The study device is a variable wattage all-in-one device, which is inclusive of the three power levels we intend to study. It is important to note that e-

5.3.2 Pre-Admission Abstinence

Participants will need to abstain from using any tobacco products starting 48 hours before each hospital visit day and any e-cigarette device the night starting each study arm, starting at 10 PM.

5.4 STUDY VISITS

5.4.1 STUDY ARM #1

5.4.1.a Out-Patient Day #1

- Participants will arrive to the hospital research ward at about 7 A.M. after overnight abstinence from e-cigarettes starting at 10 PM and 48 hours abstinence from smoking tobacco cigarettes.
- At the time of admission to the hospital ward, expired CO will be measured. Those with expired CO of 5 ppm or over will not receive the abstinence bonus. The participant will be given the option to delay study procedures until CO levels decrease or to be sent home without pay.
- Participants will be in a hospital-approved smoking room with negative pressure and a fan ventilating to the outside.
- At about 8 AM, an intravenous catheter will be placed in the forearm for blood sampling.

Standardized E-Cigarette Vaping Session

- At 9 AM, the participant will vape the study e-cigarette at the assigned power in a standardized protocol: one 4-second puff every 30 seconds for a total of 10 puffs.
- We are standardizing puff duration to minimize within- and between-subject variations in vaping topography.
- After each puff, participants will exhale into a gas trap to determine amount of nicotine exhaled.
- E-cigarettes will be weighed before and after use to determine the amount of nicotine inhaled.
- After this standardized session, the participant will abstain from using e-cigarettes for a 4-hour period.

4-hr Abstinence

- Heart rate will be measured before and at 5, 10, 15, 20, 25, and 30 minutes after product use.
- Withdrawal, craving and reward will be assessed before and immediately after the standardized session and at 2 and 4 hours after.
- Blood nicotine levels will be measured before and then at 2, 5, 15, 30, 45, 60,

- At the end of the 4-hour abstinence period, participants will be allowed 90 minutes of ad libitum access to the e-cigarette at the same assigned power level as during the standardized session.

90-minute ad libitum session

- Blood samples will be collected before and every 15 minutes from the beginning of the session.
- Withdrawal, craving, and reward will be assessed before and immediately after the session ends.
- Vaping topography (puff number, puff duration, and inter-puff interval) will be measured via digital video recordings that allow frame-by-frame analysis
- Participant will be free to go at the end of the ad-lib session, around 3:30 pm.

5.4.1.b Out-Patient Day #2

- Participants will arrive to the hospital research ward at about 7:30 A.M. with continued abstinence from smoking tobacco cigarettes.
- At arrival expired CO will be measured. Those with expired CO of 5 ppm or over will not receive the abstinence bonus. Study procedures will continue.
- Participants will wear an ambulatory blood pressure and heart rate recorder to assess circadian blood pressure, heart rate pattern, and heart rate variability (8 AM-8 PM).
- Participants will be free to vape the assigned product as they would like from 8 AM to 8 PM.
 - The time of each puff will be recorded by the participant using a mobile app (Nomie2) or paper log if app is unavailable.
- The e-cigarette will be weighed before and at the end of the day to determine the amount of e-liquid consumed, including if re-filled.
- Questionnaires to assess reward and craving and other nicotine withdrawal symptoms will be completed 4 times (8 AM, 12 noon, 4 PM and 8 PM).
- 12-Hour urine will be collected for assessment of various toxicant biomarkers and effects biomarkers.
- Blood will be sampled every four hours from 8 AM to 8 PM.
 - Nicotine will be measured in all blood samples and cardiovascular effects biomarkers will be measured in the 8 AM (pre-vaping) and 12 PM blood samples.
- Participants will be free to go home after the final blood draw and questionnaire at ~8 PM.

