Figure 1 Summary of mechanisms by which tobacco smoke constituents cause an acute cardiovascular event.

to CV events in people with pre-existing CVD, including sudden death due to arrhythmia. SNS stimulation also contributes to a more atherogenic lipid profile and insulin resistance and diabetes, which are important CVD risk factors. Depending on device and use conditions, e-cigarettes produce nanoparticles consisting of metals, metal oxides, and other

compounds. Epidemiologic studies have long linked exposure to particles in ambient air to increased risk of CVD, cancer, and respiratory diseases.

We propose to measure biomarkers of exposure to potential CV toxicants (acrolein, nicotine, and CO). We will also measure biomarkers of relevant pathogenesis mechanisms related to acute CVD (oxidant injury, inflammation, platelet activation, endothelial dysfunction and SNS stimulation; SNS stimulation is measured as increased heart rate and blood pressure and urine catecholamines). Specific biomarkers with citations are summarized in **Table 3**. These biomarkers were selected since they have been shown to change rapidly after smoking, so we can assess short-term effects, and are known to be correlated with CVD risk. Our studies of different e-cigarette power and HNB products will include all of the biomarkers presented in **Table 3**. Since e-liquid pH is expected to influence primarily nicotine exposure and pharmacokinetics, the e-liquid pH study will focus on the effects of nicotine exposure and pharmacokinetics on hemodynamic parameters and not on the other CVD biomarkers.

Table 3: Cardiovascular Risk Biomarkers	
Function	Biomarkers
Sympathetic nervous system stimulation	Heart Rate Urinary catecholamines
Oxidative stress	Urinary F2-isoprostanate
Platelet activation / Thrombosis	Urinary 11-dehydro-thromboxane B2 (11-dTXB2)
Endothelial dysfunction	Plasma Vascular Endothelial Growth Factor (VEGF)
	Plasma Intracellular Adhesion Molecule-1 (ICAM-1)
Inflammation	Plasma interleukin 6 (IL-6)

E-cigarette Power is related to Nicotine Delivery and Toxicant Generation

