2.4.2 Randomization

Participants will be assigned to begin procedures starting with one of three possible power levels using a Latin square design.

1) 10 Watts

OR

2) 15 Watts

OR

3) 20 Watts

Orientation # (N= 21)	Sequence	Study ARM 1	Study ARM 2	Study ARM 3
1	1	10W	15W	20W
2	2	15W	20W	10W
3	3	20W	10W	15W
4	4	20W	15W	10W
5	5	10W	20W	15W
6	6	15W	10W	20W
7	1	10W	15W	20W
8	2	15W	20W	10W
9	3	20W	10W	15W
10	4	20W	15W	10W
11	5	10W	20W	15W
12	6	15W	10W	20W
13	1	10W	15W	20W
14	2	15W	20W	10W
15	3	20W	10W	15W
16	4	20W	15W	10W
17	5	10W	20W	15W
18	6	15W	10W	20W
19	1	10W	15W	20W
20	2	15W	20W	10W
21	3	20W	10W	15W
22	4	20W	15W	10W
23	5	10W	20W	15W
24	6	15W	10W	20W

The participant will not be considered for assignment until it has been verified that he/she is eligible and the Eligibility Checklist has been signed. The experimental design includes a counter-balanced randomized treatment order to complete replication with total sample sizes of 21 or 24 (complete Blocks of n= 3). At the orientation visit, the participant will be assigned their treatment sequence from the above randomization schedule. In cases where a block will be incomplete because a participant has dropped out or been lost to follow up, their orientation assignment can be reused.

The final order assignment will take place at the orientation visit when the participant is physically present at the UCSF Tobacco Research Center. The CRC will refer to the "Assignment Tracking Log," input the participant's initials, product assignment, and date he/she is assigned to that condition. Assignment does not necessarily reflect the sequence of the participant's consent in the study, but rather when he/she is booked for the start of orientation. That time course will vary based upon participant, CRC and CTSI availability.

If a participant drops out or is lost to follow-up (LTFU) during the study, he/she will not be replaced. The assignment schedule will continue as assigned, and the PI can decide to enroll additional participants to compensate for non-completers.

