- Participants will be admitted to the hospital research ward at about 7 A.M after overnight abstinence from e-cigarettes starting at 10 PM and 48 hours abstinence from smoking tobacco cigarettes
- At the time of admission to the hospital ward, expired CO will be measured. Those with expired CO of 5 ppm or over will not receive the abstinence bonus. Study procedures will continue.
- Participants will wear an ambulatory blood pressure and heart rate recorder to assess circadian blood pressure, heart rate pattern, and heart rate variability (8 AM-8 PM).
- Participants will be free to vape the assigned product as they would like from 8 AM to 8 PM.
 - The time of each puff will be recorded by the participant using a mobile app (Nomie2) or paper log if app is unavailable.
- The e-cigarette will be weighed before and at the end of the day to determine the amount of e-liquid consumed, including if re-filled.
- Questionnaires to assess reward and craving and other nicotine withdrawal symptoms will be completed 4 times (8 AM, 12 noon, 4 PM and 8 PM).
- 12-Hour urine will be collected for assessment of various toxicant biomarkers and effects biomarkers.
- Blood will be sampled every four hours from 8 AM to 8 PM.
 - Nicotine will be measured in all blood samples and cardiovascular effects biomarkers will be measured in the 8 AM (pre-vaping) and 12 PM blood samples.
- Participants will be free to go home after the final blood draw and questionnaire at ~8 PM.

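### The protocol gives conflicting e-cigarette abstinence rules for the night before Day 2, so the 8 AM plasma biomarker baseline may not be abstinent in Period 1

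*Protocol*

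**What the plan says.** Four places in the Protocol bear on e-cigarette use during the night between Day 1 and Day 2 of an arm.

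- Section 5.3.2 requires abstinence from "any e-cigarette device the night starting each study arm, starting at 10 PM". It says nothing about the second night.
- Section 5.4.1.b (Arm 1, Day 2): "Participants will arrive to the hospital research ward at about 7:30 A.M. with continued abstinence from smoking tobacco cigarettes". E-cigarettes are not mentioned.
- Sections 5.4.2.b and 5.4.3.b (Arms 2 and 3, Day 2): admission "at about 7 A.M after overnight abstinence from e-cigarettes starting at 10 PM and 48 hours abstinence from smoking tobacco cigarettes".
- Day 1 ends in mid-afternoon in every arm: "Participant will be free to go at the end of the ad-lib session, around 3:30 pm". The night is therefore unsupervised.

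On Day 2 of every arm, "cardiovascular effects biomarkers will be measured in the 8 AM (pre-vaping) and 12 PM blood samples". Nicotine is also assayed at 8 AM: "Nicotine will be measured in all blood samples". The participant schedule in section 5.4.4 lists the same Day 2 procedures for all three arms and does not settle the difference.

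**The concern.** The rules cannot all be intended. Either Arm 1 and section 5.3.2 omit a requirement, or the Arm 2 and 3 wording was carried over from Day 1 by mistake. Staff who follow the text would instruct participants differently in Period 1 than in Periods 2 and 3.

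The 8 AM Day 2 sample is the only stated baseline for plasma IL-6, ICAM-1 and VEGF, which serve Hypothesis 1c. The background text before Table 3 says of the biomarker set: "These biomarkers were selected since they have been shown to change rapidly after smoking, so we can assess short-term effects". If that holds for vaping, use shortly before arrival could move the baseline. It would then differ between periods, and a change from 8 AM to 12 PM would be noisier. Heart rate, craving, withdrawal and nicotine are less exposed, because they also have a Day 1 baseline taken after abstinence.

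**Working it through.** The protocol gives no figure to reproduce on this point. The check compares the intervals the text allows, looks at balance over periods, and then sizes the noise under stated assumptions.

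**1. Shortest e-cigarette-free interval before the 8 AM Day 2 sample**

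| Reading | Arm 1 | Arms 2 and 3 |
|---|---|---|
| Each arm's own section followed | 7:30 to 8 AM = about 0.5 h | 10 PM to 8 AM = 10 h |
| Section 5.3.2 governs throughout | about 0.5 h | 7 to 8 AM = about 1 h |

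On the first reading one period in three is affected: 24 of 72 baselines at N = 24, or 21 of 63 at N = 21, if everyone completes.

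**2. Could the 48-hour tobacco rule close the gap?** No. Section 5.3.2 lists e-cigarettes separately from tobacco products, and a 48-hour e-cigarette ban before Day 2 would forbid the vaping that Day 1 requires.

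**3. Balance.** Section 2.4.2 states: "The experimental design includes a counter-balanced randomized treatment order to complete replication with total sample sizes of 21 or 24". Counting its schedule, 10, 15 and 20 W each fall in Period 1 for 8 participants at N = 24 and for 7 at N = 21. The counts are the same in Periods 2 and 3.

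**4. Effect on the 20 W minus 10 W contrast in the 8 AM to 12 PM change.** Let b be an assumed upward shift of the Period 1 baseline, and SD the standard deviation of the within-person difference. The shift lowers the Period 1 change by b, so the within-person difference moves by:

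- +b if 10 W came first,
- −b if 20 W came first,
- 0 if 15 W came first.

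Each case is one third of participants. The mean is (b − b + 0)/3 = 0, so there is no bias. The mean square is (b² + b² + 0)/3 = (2/3)b².

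If a share p of participants shift, the estimated contrast variance is multiplied by:

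- period not modelled: 1 + (2/3) p (b/SD)²
- period modelled: 1 + (2/3) p (1 − p) (b/SD)²

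| p | b/SD | Period not modelled | Period modelled |
|---|---|---|---|
| 1 | 0.25 | 1 + (2/3)(0.0625) = 1.042 | 1.000 |
| 1 | 0.5 | 1 + (2/3)(0.25) = 1.167 | 1.000 |
| 0.5 | 0.25 | 1 + (2/3)(0.5)(0.0625) = 1.021 | 1 + (2/3)(0.25)(0.0625) = 1.010 |
| 0.5 | 0.5 | 1 + (2/3)(0.5)(0.25) = 1.083 | 1 + (2/3)(0.25)(0.25) = 1.042 |

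A simulation with participant effects (N = 24, 4000 runs per setting) agreed with these factors to within 0.01 and showed no bias beyond simulation error. The values of b and p are illustrations; the protocol gives neither.

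**5. When the zero-bias result fails.** It needs overnight use to be unrelated to the Day 1 power. If the mean baseline shift is b10 after 10 W and b20 after 20 W, the contrast is biased by (b10 − b20)/3 when only Period 1 is affected, because each power sits there for one third of participants. It is biased by b10 − b20 when all periods are affected.

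**The case against.** The strongest reply concerns weight rather than fact. The wording differs, but the power contrasts stay unbiased and the remaining noise is small. With period modelled the largest factor above is 1.04, worth about one participant in 24 (24 × 0.04 ≈ 1). The 1.17 needs every participant to shift by half an SD and an analysis that ignores period, and the analysis plan is not shown. The half-hour interval is the extreme the text allows, not a typical case. Nor does the protocol say that the change from 8 AM is what will be analysed.

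Two further points are fair. The label pre-vaping may mean only before the 8 AM start of free use, so it does not itself contradict the missing rule. And the statement about rapid change covers all of Table 3 after smoking; it does not show that these three plasma markers respond to a short spell of vaping. Even the 10 PM rule gives a baseline about 10 hours after last use, not an unexposed one.

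These points limit the size of the problem, but the conflict between the rules remains. Analysis cannot recreate an abstinent baseline; the 8 AM nicotine value only shows part of what happened. Two considerations run the other way. Ambulatory monitoring and the 12-hour urine occur only on Day 2, so they have no Day 1 measurement to fall back on either. And dropouts are not automatically replaced (section 2.4.2), so the balance may not be complete.

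**Conclusion.** The concern holds. The current text contains two incompatible rules for the night before Day 2, and nothing in it resolves them. As written, the minimum e-cigarette-free interval before the 8 AM sample is about 0.5 h in Period 1 and 10 h in Periods 2 and 3; if section 5.3.2 governs, it is about 0.5 to 1 h throughout. The main consequence is a baseline for IL-6, ICAM-1 and VEGF that may not be comparable across periods. The absence of bias in the power contrasts rests on complete blocks and on overnight use that does not depend on power. The loss of precision is modest, rests on assumed shifts, and matters only if the baseline enters the analysis. The protocol should be corrected, but this does not threaten the trial's main comparisons.

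**What to change.** - In section 5.3.2, require e-cigarette abstinence from 10 PM on the night before each hospital visit day, not only the night that starts an arm.
- Align the abstinence wording in section 5.4.1.b with sections 5.4.2.b and 5.4.3.b, and give one Day 2 arrival time for all arms.
- Record the time of last e-cigarette use at Day 2 arrival, to be read with the 8 AM plasma nicotine.

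If the sponsor in fact intends no rule for the second night, sections 5.4.2.b and 5.4.3.b should be changed instead. The 8 AM sample should then be described as taken before the free-use session, not as an abstinent baseline. The 10 PM rule is preferable because it gives the same minimum interval in every period.

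The cost is a wording change in two sections and one case report form field, with no extra participants, visits or assays.

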4.2 PHONE EVALUATION & E-CONSENT (SCRIPT)

Individuals who are preliminarily eligible based on results from the Online Screening will be contacted for a phone evaluation to further determine eligibility prior to scheduling an in-person Screening Visit.

The procedures for the e-consent are as follows:

- CRC and participant engage in consent discussion over the phone. During this discussion CRC will review purpose, procedures, risks/benefits and alternatives. CRC will ask questions to assess the understanding of the participant.
- Participant is sent the consent powerpoint to review via email
- Participant is sent the consent form to sign in Docusign (after signing, CRC will immediately sign in Docusign and download e-consent to save on study server)
- The CRC will update the participant enrollment log assigning them a Study ID.
- Approximately 24-hours before coming in for the study visit, participant is sent the screening packet to complete online via REDCap.
 - In REDCap, CRC will add new record, assign the study ID and send the survey link directly from the REDCap system
- At the screening visit, participant signs one wet copy of the consent form (to be given to 5B research ward)
- At the screening visit, participant signs 2 HIPPA forms; one for research ward 5B and one for the study team
- At the screening visit, participant will be presented with the Bill of Rights
- Participant will also be presented with the vaping safety handout.

The script for the phone evaluation is as follows:

Phone Evaluation Scripts

Various items related to eligibility must be confirmed by the CRC during a phone conversation.

ALL participants will be asked, *“Are you willing to use a mod e-cigarette for this study?”*

ALL participants will be asked *“Are you allergic to propylene glycol or vegetable glycerin?”*

These following questions will also be asked ***if applicable:***

If participants indicate they are in a drug treatment program, *“I saw you indicated that you are in a drug treatment program. Can you let me know what that is for?”*

OR

“I see that you have listed [methadone] [buprenorphine] as current medications. Can you let me know what that is for?”

If participant uses other tobacco products, *“As part of this study we will ask you to*

avoid other tobacco products like cigarillos, blunts, etc. from the time before your hospital visit through the end of the study period. Are you okay with avoiding these for this amount of time?"

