And finally, we will be collecting personal information from you, so there is a risk of break of confidentiality. However, we will do our best to keep your confidentiality.

Can I answer any questions about risks?

Okay, let's talk about the benefits. There are no direct benefits to you, but you will be helping us learn about how vaping at low, medium, and high power levels changes how the body is exposed to nicotine and what effects the e-cigarette has on the heart. Which has great potential benefits to other vapers like you. We will also be reimbursing you for your time and effort – if you complete all parts of the study, you will be paid for each study visit and be given a completion bonus. If you complete all parts of the study, you'll get up to \$1,890 for your time and effort. Most of your payment will be processed at the very end.

Can I answer any other questions you might have? (If yes, answer) (If no, proceed)

Okay, can I ask you a few questions?

Do you remember – how long does this study last? (6 total outpatient hospital study days. 8 days total including Screening Visit and Orientation)

Do you remember – how many days will you be expected to stay at the hospital? (6 days total; 2 consecutive outpatient days per Study Arm)

What are some risks you may experience? (Discomfort, bruising, mood changes, breach of confidentiality)

Do you think you are interested in seeing if you are a match for the study?

(If yes) "Great! I am going to send you a PowerPoint presentation via your email. Please look it over – it describes in great detail more information about the study. I will also send you the consent form – please take time to read it over and review carefully. If you agree to participate, you will be prompted to sign the form electronically."

I can schedule you for the next phase of screening – this is a 45 minute screening visit. When would be a good time for you to come in for that?

(Proceed with scheduling visit)

Okay, very important before you come in...

After you sign the consent form and about 24 hours before your visit, I will send you a survey link to your email. It's important that you complete this survey before you come in, otherwise you will need to complete it in person and the visit will take longer than 45 minutes.

At the screening visit we will first review a HIPAA form. This is another important form for you to

Short-Term Cardiovascular Effects of E-Cigarettes: Influence of Device Power
IRB# 17-23965

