6.3 PROTOCOL DEVIATIONS & VIOLATIONS

Protocol deviations are defined as an event that deviates from the defined study protocol, but does not pose any risk to the participant or harm to the quality of the study data. For example, a follow-up call may be conducted outside of the stipulated window, or a section of questions on a questionnaire may be missed due to a mistake in branching. Deviations will be recorded on a protocol deviation sheet and reviewed and signed by the PI.

Protocol violations are events that deviate from the defined study protocol, but put the participant at risk and/or cause harm to the study data. Protocol violations will be recorded on a protocol violation sheet, reviewed and signed by the PI and reported to the IRB

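### Does letting Day 2 go ahead after a failed carbon monoxide check undermine the toxicant and cardiovascular biomarkers?

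*Protocol*

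**What the plan says.** Protocol 5.3.2 sets the abstinence rule: "Participants will need to abstain from using any tobacco products starting 48 hours before each hospital visit day". Expired CO at arrival is the check on both days of every arm, and 5 ppm or over loses that day's abstinence bonus. In Table 2 of section 5.5 the bonus is $40 for each day.

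The further consequence differs by day.

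- **Day 1** (5.4.1.a, 5.4.2.a, 5.4.3.a): "The participant will be given the option to delay study procedures until CO levels decrease or to be sent home without pay".
- **Day 2** (5.4.1.b, 5.4.2.b, 5.4.3.b): "Those with expired CO of 5 ppm or over will not receive the abstinence bonus. Study procedures will continue".

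The samples for Hypothesis 1b and most of Hypothesis 1c come from Day 2. For urine: "12-Hour urine will be collected for assessment of various toxicant biomarkers and effects biomarkers". For blood: "cardiovascular effects biomarkers will be measured in the 8 AM (pre-vaping) and 12 PM blood samples". The schedule in 5.4.4 also lists the 12-hour urine under Day 2 only. The two days follow each other, described in the 4.2 script as "2 consecutive outpatient days per Study Arm".

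Section 6.3 covers departures from protocol. Deviations are recorded and signed by the PI. The more serious class also goes to the IRB and is defined thus: "Protocol violations are events that deviate from the defined study protocol, but put the participant at risk and/or cause harm to the study data".

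**The concern.** The same reading at the same threshold holds up Day 1 but not Day 2, and Day 2 supplies six of the seven markers in Table 3 (all but heart rate) plus the VOC metabolites. People who smoke up to 10 cigarettes a day are eligible (2.3.1), and participants are away from the ward overnight between the two days. The background section says the cardiovascular markers were chosen because they respond quickly to smoking. Plasma has a pre-vaping sample on the same day, but no pre-vaping urine is described. No sentence says whether samples taken after a failed Day 2 check are kept, marked or set aside.

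There is also a timing point. If a participant fails on Day 1, waits a few hours and then proceeds, Day 2 begins about a day later, too soon for 48 smoke-free hours.

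At stake would be extra noise in the comparison of 10, 15 and 20 W and, if lapses depended on the power level, bias in it.

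**Working it through.** **1. Do the two rules conflict?** They apply to different days with different content. Day 1 contains a timed 10-puff session with serial nicotine and heart-rate measurements from a pre-use baseline. Day 2 is 12 hours of free use. A rule that holds up the first and lets the second run is coherent, and it is worded identically in all three arms. Section 2.4.2 says that a participant who drops out is not replaced (though the PI may enrol more), which is a plausible reason to keep a second day once the first is done. The protocol does not give its reason, but a choice without a stated reason is not a contradiction.

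**2. Would a failed Day 2 check be known?** CO is measured at every arrival and the bonus depends on the result for that day. The compensation total confirms that the bonus is counted by day: 30 + 3 × (40 + 40) + 3 × 420 + 360 = $1,890, as Table 2 states. A breach of 5.3.2 is a departure from protocol, so 6.3 already requires a record. Section 6.3 need not name every trigger.

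**3. The 48-hour timing.**

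- Arm 1: 7:00 AM on Day 1 to 7:30 AM on Day 2 is 24.5 h, so smoking in the last 48 − 24.5 = 23.5 h before Day 1 arrival falls inside Day 2's 48-hour window.
- Arms 2 and 3: 7:00 AM to 7:00 AM is 24 h, leaving 24 h.

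The arithmetic is right if the delay ends the same day, but the protocol does not say how long a delay may last. Waiting for CO to fall does not restore 48 smoke-free hours on Day 1 either. On both days the text therefore describes how someone who has already broken the abstinence rule is handled. That does not make the rule inconsistent.

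**4. How large could the effect be?** The documents give no lapse rate, fold rise, SD or true ratio, so every input here is assumed: n = 21, a true 20 W/10 W ratio of 1.5, within-person SD *s* per visit on the log scale, and a two-sided paired t-test at 0.05.

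Without lapses the variance of the paired log difference is 2*s*². Independent lapses with probability *p* that multiply the marker by *r* add 2*p*(1 − *p*)(ln *r*)². For *s* = 0.35, *p* = 0.10 and *r* = 2:

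- without lapses: 2 × 0.35² = 0.245
- added by lapses: 2 × 0.10 × 0.90 × 0.693² = 0.086
- SD of the difference: √0.245 = 0.495 rises to √0.331 = 0.576

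Simulated power (20,000 runs per scenario):

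| SD per visit | Rise | No lapses | 2% | 5% | 10% |
|---|---|---|---|---|---|
| 0.35 | 1.25× | 0.95 | 0.95 | 0.94 | 0.94 |
| 0.35 | 1.5× | 0.95 | 0.94 | 0.93 | 0.92 |
| 0.35 | 2× | 0.95 | 0.93 | 0.90 | 0.87 |
| 0.35 | 4× | 0.95 | 0.87 | 0.77 | 0.64 |
| 0.5 | 1.5× | 0.70 | 0.70 | 0.69 | 0.68 |
| 0.5 | 2× | 0.70 | 0.68 | 0.67 | 0.64 |
| 0.5 | 4× | 0.70 | 0.64 | 0.58 | 0.49 |

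If the same people lapse in both arms, the rise cancels within person and power stays at 0.94 to 0.95 (SD 0.35).

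**5. Bias.** The estimated ratio is 1.5 × *r*^(*p*20 − *p*10), where *p*20 and *p*10 are the lapse rates at 20 W and 10 W. Equal rates give 1.5 exactly. With 10% at 10 W and 5% at 20 W, a 2-fold rise gives 1.5 × 2^(−0.05) = 1.45; the reverse gives 1.5 × 2^(0.05) = 1.55. Nothing in the documents suggests such a difference.

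**6. Would excluding flagged samples be better?** At 10% lapses, SD 0.35 and a perfect flag, exclusion gives power of about 0.88 whatever the rise. Keeping all data gives 0.92 at 1.5×, 0.87 at 2× and 0.64 at 4×. Exclusion therefore loses, draws or wins according to the unknown rise. It also selects on behaviour after randomisation.

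**The case for a change.** The strongest opposing case has three parts.

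- **The rules protect the wrong day.** The stricter rule covers the day without the toxicant samples, and no reason is given. It is true that no reason is given, and that the urine has no same-day baseline. But the background remark about rapid change refers to the Table 3 markers, which do not include VOC metabolites. It also says nothing about how long an overnight cigarette would show in urine collected from 8 AM to 8 PM.
- **The Day 1 delay can produce a Day 2 visit that breaks the 48-hour rule even with a clean CO.** This is possible on a same-day delay. It shows that CO is an imperfect check of 48 hours, as it already is on Day 1. It does not put two instructions in conflict.
- **A flag and an analysis with and without flagged visits would cost little.** That is fair. At assumed lapse rates of 2%, 5% and 10%, the number of failed checks would be 63 × 0.02 = 1.3, 63 × 0.05 = 3.2 and 63 × 0.10 = 6.3 of 63 person-arms. But this is data handling and sensitivity analysis, which commonly sit in the SAP, and the suggestion would leave the Day 2 rule as it is.

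What stands is a request for one explanatory sentence on why the two days differ. That is a courtesy to the reader and does not correct an error.

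**Conclusion.** The concern does not hold. The protocol states the Day 2 rule clearly and repeats it without variation. It measures CO at each arrival, ties a bonus to each result and has a general duty to record departures. The part that seems to be missing, namely how samples after a failed check are analysed, cannot be counted as missing while the SAP is not shown.

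No worse result is demonstrated. On assumed inputs the power loss is at most 0.03 for rises up to 1.5-fold and 0.08 for a 2-fold rise (SD 0.35, n = 21, up to 10% independent lapses). It becomes material only for a 4-fold rise, and it vanishes when the same people lapse in every arm. Bias requires lapse rates that differ by power level.

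The conclusion rests on reading the Day 2 rule as deliberate, which its identical wording in three arms supports. A documented high lapse rate that differed by power level, together with a large rise in the markers, would reopen the question. The protocol contains no evidence of either.
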